2.2.3 Objectives during the open-label extension

- To evaluate the safety and tolerability of LCZ696 treatment during the OLE epoch
- To assess the proportion of patients reaching target dose level 3 of LCZ696 at Week 8 and maintained at Month 4

- To assess the effect of LCZ696 on change in NYHA classification from OLE baseline (Visit 301) at Month 12
- To assess the effects of LCZ696 on change in cardiac measurements by echocardiography (LV end systolic and diastolic volume indices, LVEF, and LA volume index, etc.) from OLE baseline (Visit 301) at Month 12
- To assess the effects of LCZ696 on changes in pre-specified biomarkers from OLE baseline (Visit 301) to predefined timepoints (Weeks 2-4, 8, Month 4 and 12)
- To assess the association between change in concentration of NT-proBNP and change in structural cardiac measurements (LV end systolic and diastolic volume indices, LVEF, and LA volume index) from OLE baseline (Visit 301) at Month 12
- To assess the effects of long-term treatment with LCZ696 on the safety and tolerability throughout the study period

[REDACTED]

[REDACTED]

[REDACTED]

[REDACTED]

3 Investigational plan

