a The patient receiving double-blind study drug at dose level 2 has options to start with either the open-label LCZ696 100 mg b.i.d. (dose level 2) or LCZ696 50 mg b.i.d. (dose level 1) at the investigator's discretion.

Table 3-3 Safety monitoring criteria for up-titration at Visit 302 (Week 2 to 4)

Parameter	Visit 302 (Week 2 to 4)
Serum potassium level	$K \leq 5.4 \text{ mmol/L (mEq/L)}$ (local assessment)
Kidney function	$eGFR \geq 30 \text{ mL/min/1.73 m}^2$ $eGFR \text{ reduction} \leq 35\% \text{ compared to Visit 301}$ (local assessments)
Blood pressure	No symptomatic hypotension and $SBP \geq 95 \text{ mmHg}$.
AEs or conditions	No postural symptoms or any AEs that preclude continuation according to the investigator's judgment

OLE epoch initiation visit (Visit 301)

All patients must provide informed consent before any study-specific procedure for OLE epoch is performed. At Visit 301, patients' eligibility for entering the OLE epoch will be assessed by the investigator.

Patients will start the OLE epoch at this visit. This first visit of the OLE epoch will occur on the same day as the end of study (EOS) visit of the core part. Patients will be switched to an open-label LCZ696 at this visit. The patients receiving double-blind study drug at dose level 3 will start with open-label LCZ696 100 mg b.i.d. (dose level 2) ([Table 3-2](#)). The patients receiving double-blind study drug at dose level 2 will start with either open-label LCZ696 50 mg b.i.d. (dose level 1) or LCZ696 100 mg b.i.d. (dose level 2) at the investigator's discretion. The patients receiving double-blind study drug at dose level 1 will be also switched to an open-label LCZ696 but remain at same dose level (LCZ696 50 mg b.i.d.) up to Visit 302. Patients should continue to take their background medications for HF, with the exception of ACEIs or ARBs. The patients who have discontinued the double-blind study drug before this visit may be enrolled if eligible, however, should start with taking the LCZ696 50 mg b.i.d. (dose level 1).

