4.1 Inclusion criteria

Patients eligible for inclusion in the core part have to fulfill all of the following criteria:

1. Written informed consent must be obtained before any assessment is performed.
2. Outpatients ≥ 20 years of age (at the time of signing informed consent), male or female.
3. Patients with a diagnosis of CHF NYHA class II-IV and reduced ejection fraction:
 - LVEF $\leq 35\%$ at Visit 1 (any local measurement, made within the past 6 months using echocardiography, MUGA, CT scanning, MRI or ventricular angiography is also acceptable, provided no subsequent measurement above 35%)
 - NT-proBNP ≥ 600 pg/ml at Visit 1 **OR** NT-proBNP ≥ 400 pg/ml at Visit 1 and a hospitalization for HF within the last 12 months (according to central laboratory measurements)
4. Patients must be on an ACEI or an ARB at a stable dose for at least 4 weeks before Visit 1.
5. Patients must be treated with a β -blocker, unless contraindicated or not tolerated, at a stable dose for at least 4 weeks prior to Visit 1 (reason should be documented if patients reported contraindications or intolerance).
6. An aldosterone antagonist should also be considered in all patients, taking account of renal function, serum potassium and tolerability. If given, the dose of aldosterone antagonist

should be optimized according to guideline recommendations and patient tolerability, and should be stable for at least 4 weeks prior to Visit 1. Other evidence-based therapy for HF should also be considered e.g. cardiac resynchronization therapy and an implantable cardioverter-defibrillator in selected patients, as recommended by guidelines.

Patients eligible for inclusion into the open-label extension must fulfill the following criteria:

7. Written informed consent for the open-label extension must be obtained before any assessment is performed.
8. Patients who have completed the double-blind treatment epoch and are able to be safely enrolled into the OLE as judged by the investigator.

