 - Female sterilization (have had surgical bilateral oophorectomy with or without hysterectomy) or tubal ligation at least 6 weeks before taking study treatment. In case of oophorectomy alone, only when the reproductive status of the woman has been confirmed by follow up hormone level assessment.
 - Male sterilization (at least 6 months prior to screening). For female subjects on the study, the vasectomized male partner should be the sole partner for that subject.

- Combination of any two of the following (a+b, a+c or b+c):
 - a. Use of oral, injected* or implanted* hormonal methods of contraception or other forms of hormonal contraception that have comparable efficacy (failure rate < 1%), for example hormone vaginal ring or transdermal hormone contraception*.
 - b. Placement of an intrauterine device (IUD) or intrauterine system (IUS)
 - c. Barrier methods of contraception: Condom or Occlusive cap (diaphragm or cervical/vault caps*) with spermicidal foam*/gel*/film*/cream*/vaginal suppository*

*: not approved in Japan, approved methods should be used.

In case of use of oral contraception women should have been stable on the same pill for a minimum of 3 months before taking study treatment.

Women are considered post-menopausal and not of child bearing potential if they have had 12 months of natural (spontaneous) amenorrhea with an appropriate clinical profile (e.g., age appropriate, history of vasomotor symptoms) or have had surgical bilateral oophorectomy (with or without hysterectomy) or tubal ligation at least 6 weeks ago. In the case of oophorectomy alone, only when the reproductive status of the woman has been confirmed by follow up hormone level assessment is she considered not of child bearing potential.

Patients fulfilling any of the following criteria at Visit 301, are not eligible for inclusion in the OLE epoch. No additional exclusions may be applied by the investigator.

26. Patients who discontinued study drug treatment during the core part due to an event or intercurrent illness. Eligibility can be re-considered if the event has resolved and no longer represents a risk to the patient and the patient can safely tolerate the administration of LCZ696 per the investigator's assessment.
27. Any medical condition that in the opinion of the investigator is likely to prevent the patient from safely tolerating LCZ696 or complying with the requirements of the study.

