28. Patients who have experience of angioedema event(s) which occurred and reported by the investigator during the core part of study.
29. Pregnant or nursing (lactating) women, where pregnancy is defined as the state of a female after conception and until the termination of gestation, confirmed by a positive hCG laboratory test.
30. Women of child-bearing potential, defined as all women physiologically capable of becoming pregnant, unless they are using highly effective methods of contraception while taking study treatment and for 7 days after stopping study treatment. Highly effective contraception methods include:
 - Total abstinence (when this is in line with the preferred and usual lifestyle of the subject. Periodic abstinence (e.g., calendar, ovulation, symptothermal, post-ovulation methods) and withdrawal are not acceptable methods of contraception
 - Female sterilization (have had surgical bilateral oophorectomy with or without hysterectomy), total hysterectomy or tubal ligation at least 6 weeks before taking study treatment. In case of oophorectomy alone, only when the reproductive status of the woman has been confirmed by follow up hormone level assessment.

- Male sterilization (at least 6 months prior to Visit 301). For female subjects on the study, the vasectomized male partner should be the sole partner for that subject.
- Use of oral, injected* or implanted* hormonal methods of contraception or placement of an intrauterine device (IUD) or intrauterine system (IUS), or other forms of hormonal contraception that have comparable efficacy (failure rate < 1%), for example hormone vaginal ring or transdermal hormone contraception*.

*: not approved in Japan, approved methods should be used.

In case of use of oral contraception women should have been stable on the same pill for a minimum of 3 months before taking study treatment.

Women are considered post-menopausal and not of child bearing potential if they have had 12 months of natural (spontaneous) amenorrhea with an appropriate clinical profile (e.g. , age appropriate history of vasomotor symptoms) or have had surgical bilateral oophorectomy (with or without hysterectomy), total hysterectomy, or tubal ligation at least 6 weeks ago. In the case of oophorectomy alone, only when the reproductive status of the woman has been confirmed by follow up hormone level assessment is she considered not of child bearing potential.

5 Treatment

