9.1 Analysis sets

The following populations will be used for the core part statistical analyses:

The Screened Set (SCR) will consist of all patients who signed the informed consent. The screened set includes only unique screened patients, i.e., in the case of re-screened patients only the chronologically last screening data is counted.

The Enrolled Set (ENR) (run-in epoch) will consist of all patients who received at least one dose of run-in study medication.

The Randomized Set (RAN) will consist of all patients who received a randomization number, regardless of receiving double-blind investigational drug.

The Full Analysis Set (FAS) will consist of all randomized patients with the exception for those patients who have not been qualified for randomization and have not received investigational drug, but have been inadvertently randomized into the study. Following the intent-to-treat principle, patients will be analyzed according to the treatment to which they were assigned at randomization. Efficacy variables will be analyzed based on the FAS as the primary population.

The Safety Population (SAF) will consist of all randomized patients who received at least one dose of double-blind medication. Patients will be analyzed according to the treatment actually received. The safety population will be used for the analyses of safety variables.

The Per-protocol (PP) population will be a subset of the FAS which will consist of the patients who do not have major deviations from the protocol procedures in the double-blind study stage. Major protocol deviations will be pre-specified prior to un-blinding treatment codes for analyses. This supplemental efficacy population will be used to support the primary analysis results.

The following populations will be used for the OLE statistical analyses:

The Extension Population (EXT): All eligible patients who have completed the core part and have signed the informed consent for the OLE epoch.

The Full Analysis Set for OLE epoch (FAS-Ext): All patients who receive at least one dose of the extension study drug. The FAS-Ext population is the analysis set for both safety and efficacy analysis.

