9.5.2 Safety variables

The safety and tolerability assessments are listed below:

- AEs and SAEs
- Sitting systolic, diastolic BP, and pulse pressure
- Heart rate
- Symptomatic hypotension and/or SBP < 90 mmHg
- Angioedema
- Hyperkalemia
- Renal dysfunction
- Cough
- Drug-related hepatic disorders
- Other relevant laboratory values
- ECG changes

The assessment of safety will be based primarily on the frequency of adverse events, SAEs, and laboratory abnormalities. Other safety data will be summarized as appropriate.

The incidence of treatment-emergent adverse events (new or worsened) will be summarized by primary system organ class, preferred term, severity, and relationship to study drug. In addition, the incidence of death, SAEs, and AEs leading to discontinuation will be summarized separately by primary system organ class and preferred term.

Laboratory data will be summarized by presenting shift tables using extended normal ranges (baseline to most extreme post-baseline value), by presenting summary statistics of raw data and change from baseline values (mean, medians, standard deviations, ranges) and by the flagging of notable values in data listings.

Data from other tests (e.g., ECG or vital signs) will be listed, notable values will be flagged, and any other information collected will be listed as appropriate.

Safety analyses will be performed based on the safety population. There will be no formal statistical inference analysis.

In addition to the above safety analyses for the randomized double-blinded treatment epoch, the AEs, SAEs, and reasons for active run-in failures will be summarized for the active run-in epoch.

One cut-off data analysis will be carried during the OLE epoch after all patients have been enrolled into the OLE, and completed Visit 304 (Month 4) or discontinued.

The cut-off date is defined as the latest of Visit 304 date or discontinuation date (the last visit prior to Visit 304). All data on or prior to this cut-off date during the OLE epoch will be used for analysis. All specified safety analyses in this section will be performed for this cohort.

For AEs/SAEs, FAS-Ext will be used, and all analyses will be done for total, and by the treatment arm in the double-blind treatment epoch. Additionally, all analyses will be repeated for subset of FAS-Ext with only patients in LCZ arm of double blind treatment epoch, throughout the period from run-in epoch to OLE epoch.

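### The run-in-to-OLE adverse event analysis of LCZ696 includes only patients who reached the extension, so it cannot show a death from the core part

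*Protocol*

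**What the plan says.** Protocol section 9.5.2 summarizes OLE adverse events on FAS-Ext, in total and by double-blind arm. It then adds that "all analyses will be repeated for subset of FAS-Ext with only patients in LCZ arm of double blind treatment epoch, throughout the period" running from run-in into the OLE. Among the AE analyses set out earlier in that section, "the incidence of death, SAEs, and AEs leading to discontinuation will be summarized separately by primary system organ class and preferred term".

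Who can be in the set is fixed elsewhere:

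- Section 9.1 defines FAS-Ext as "All patients who receive at least one dose of the extension study drug".
- Section 4.1, criterion 8, admits to the OLE "Patients who have completed the double-blind treatment epoch and are able to be safely enrolled into the OLE", in the investigator's judgment.
- Section 4.2, criterion 28, excludes "Patients who have experience of angioedema event(s) which occurred and reported by the investigator during the core part of study".
- Section 4.2, criterion 26, excludes "Patients who discontinued study drug treatment during the core part due to an event or intercurrent illness", but allows this to be reconsidered once the event has resolved. Section 3.1.1.4 likewise says: "The patients who have discontinued the double-blind study drug before this visit may be enrolled if eligible".

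The related objective in section 2.2.3 is: "To assess the effects of long-term treatment with LCZ696 on the safety and tolerability throughout the study period".

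**The concern.** Membership of the set is settled only at the start of the OLE, but events are counted back to run-in. For death, all of a member's core-part time is immortal time: the patient had to survive it to be counted. The table heading would cover run-in, core part and OLE, while deaths could arise only in the last of these.

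A reader who takes the display as the whole-period LCZ696 safety summary would see no core-part deaths and could take that as a finding about the drug. If criterion 28 is followed, the same holds for investigator-reported core-part angioedema, an event the protocol singles out for adjudication.

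**Working it through.** The protocol gives no figure for this analysis that could be reproduced. The check is one of set membership, followed by an illustration of size.

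**Step 1: what the set can contain.**

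| Core-part event in the LCZ696 arm | Can it appear in the run-in-to-OLE display? | Reason |
|---|---|---|
| Death | No, by definition | No extension dose is possible (9.1) |
| Investigator-reported angioedema | No, if criterion 28 is followed | FAS-Ext is defined by dosing alone, so this zero depends on compliance |
| Event leading to permanent stop of study drug | Yes, but probably depleted | Criterion 26 excludes, with an exception; section 3.1.1.4 admits eligible discontinuers |
| Other non-fatal AE or SAE | Yes, for OLE entrants only | Patients outside the OLE contribute nothing |

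**Step 2: how many patients are left out.** Section 4 plans about 220 randomized patients (110 per arm) and about 180 core-part completers, most of whom are expected to enter the OLE.

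- Non-completers: 220 - 180 = 40, and 40/220 = 18.2%. Completers who decline the OLE add to this.
- LCZ696 arm, even split assumed: 40/2 = 20, and 20/110 = 18.2%.
- LCZ696 arm, assumed range of 15 to 25: 15/110 = 13.6% to 25/110 = 22.7%.

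Under sections 3.1.1.3 and 5.5.9, stopping study drug in the double-blind epoch is not withdrawal from the study. These non-completers are therefore mainly deaths, withdrawn consents and losses to follow-up.

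**Step 3: core-part deaths.** The protocol gives no mortality figure, so the share of non-completers who died is assumed. All 110 patients are taken as dosed, so that 110 stands for the LCZ696-arm Safety Population.

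| LCZ696 non-completers | Share who died | Core-part deaths | Incidence in 110 | Incidence in the display |
|---|---|---|---|---|
| 20 | 25% | 5 | 4.5% | 0% |
| 20 | 50% | 10 | 9.1% | 0% |
| 20 | 75% | 15 | 13.6% | 0% |
| 15 | 25% | 3.75 | 3.4% | 0% |
| 25 | 75% | 18.75 | 17.0% | 0% |

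**Step 4: a second route to the same size.** Assume a constant all-cause death rate r per patient-year, with no other dropout. Section 9.7 gives R = 22/12 years of uniform accrual and a minimum follow-up of F = 18/12 years. The expected proportion dying in the core part is 1 - [exp(-rF) - exp(-r(F+R))]/(rR).

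- r = 0.02: 4.7%, about 5 of 110
- r = 0.04: 9.2%, about 10 of 110
- r = 0.06: 13.5%, about 15 of 110
- r = 0.08: 17.5%, about 19 of 110

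The rates are assumptions. The range agrees with step 3.

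**Step 5: share of the displayed period in which a death can be counted.** Section 3.1 expects an average core follow-up of about 28.5 months. At the OLE cut-off (Month 4) the share is roughly 4/(28.5 + 4) = 12%. With 24 months of OLE it is 24/(28.5 + 24) = 46%.

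**The case against.** The strongest reply is that nothing is lost from the report. Section 9.5.2 puts core-part deaths, SAEs and discontinuations on the Safety Population, summarizes run-in AEs and run-in failures separately, and summarizes OLE events on FAS-Ext. Every epoch is covered. The display at issue is supplementary, names its own subset, and belongs to a section with no formal inference. The objective sits under the OLE heading and does not ask for one pooled table. Following the full course of patients who stayed on LCZ696 into the extension is a common choice, and labels and period-specific rates are usually left to the SAP, which was not at hand.

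Much of this stands. It confines the defect to one descriptive display and keeps it away from the primary endpoint and core safety reporting. It is also true that only the death point is certain: the angioedema zero depends on compliance, and depletion of discontinuation events is only probable. For laboratory values, vital signs and ECG (9.5.2), NYHA class (9.5.1.3) and NT-proBNP (9.5.1.10), a fixed cohort is defensible.

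It does not answer the death point. The protocol itself fixes both the set and the window, so this is a stated rule and not detail left open. Separate epoch tables do not give a cumulative LCZ696 summary. In the visible text this display is the only whole-period AE/SAE analysis; redactions prevent a stronger statement.

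**Conclusion.** The concern holds. As specified, the run-in-to-OLE summary of LCZ696 AEs, SAEs and deaths must show zero core-part deaths, and this follows from sections 9.1, 4.1 and 9.5.2 without any assumption. OLE deaths would still appear.

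At least 18% of randomized patients are left out on the planning figures. The core-part death incidence missing from the display is 4.5% to 13.6% of the LCZ696 arm with 20 non-completers, or 3.4% to 17.0% when the arm split is varied as well. Those percentages rest on the assumed split and death shares; only 220, 110 and 180 are the protocol's. The effect on other AEs cannot be computed from the protocol.

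This should be fixed. Read alone, the display understates harm; read beside the core Safety Population tables, it loses nothing.

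**What to change.** In section 9.5.2:

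- Base the cumulative run-in-to-OLE AE, SAE and death summary on all LCZ696-arm patients in the Safety Population, whether or not they entered the OLE, with exposure-adjusted rates by period (run-in, core, OLE).
- Count deaths and SAEs over all study follow-up to the cut-off, without truncating at the end of LCZ696 exposure. Show on-treatment and post-treatment events separately, because section 5.5.6 permits open-label ACEIs or ARBs after study drug is stopped. For patients not entering the OLE, follow-up ends with the 30-day safety contact in section 6.
- State that this set is still conditional on tolerating run-in (3.1.1.2), and place the run-in summary beside it.
- Keep FAS-Ext for events arising in the OLE.

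In sections 9.5.1.3, 9.5.1.10 and 9.5.2, label every FAS-Ext display that reaches back to run-in as conditional on OLE entry. For laboratory, vital-sign, ECG, NYHA and NT-proBNP displays the label is enough.

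The cost is a short change of text in 9.5.2, the labels and extra table programming. The data are already collected. The cumulative rates may look less favourable than those from the present set. A label and a cross-reference to the Safety Population death table would be cheaper, but would leave the whole-period objective without a summary that can show core-part deaths.

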3.1.1.2 Single-blind active treatment run-in epoch

Patients who are successfully screened into the study at Visit 1 will enter the single-blind active treatment run-in epoch. Since this epoch will be a single-blind period, the site staff working with patients should exercise caution when discussing the study procedures and the study drug with patients to keep the patient blinded to the identity of the study drug.

Please refer to [Table 6-1](#) for a detailed list of study procedures and assessment to be performed at each run-in epoch visit.

Visit 101

Once patients' eligibility has been ascertained, they will attend Visit 101 approximately one to two weeks after Visit 1 to start LCZ696 50 mg b.i.d. for 2 weeks. Patients should continue to take their background medications for CHF, with the exception of ACEIs or ARBs which must be discontinued at Visit 101.

If patients meet the criteria in [Table 3-1](#), they will start to take the LCZ696 50 mg b.i.d. run-in medication the day after Visit 101. An approximately 36-48 hour wash-out period stopping concomitant ACEIs or ARBs should be included before the enrolled patients start taking the first dose of LCZ696. For example, if a patient's Visit 101 is on Wednesday, he/she must not take any doses of ACEIs or ARBs after the last dose on Tuesday. The patient will then start taking the first dose of LCZ696 50 mg b.i.d. run-in medication on Thursday morning.

End of treatment run-in visit (Visit 199)

A Visit 199 (end of treatment run-in visit) will be completed for all patients who enter the treatment run-in epoch. Patients not tolerating LCZ696 50 mg b.i.d. ([Table 3-1](#)) will be considered run-in failures and withdrawn from the study. For patients who discontinue during the treatment run-in epoch, Visit 199 will be their discontinuation visit.

Only patients who tolerate LCZ696 50 mg b.i.d. for 2 weeks will be eligible for randomization. For patients that are eligible to be randomized, Visit 199 will be their end of treatment run-in disposition visit and may be performed on the same day as Visit 201. [Table 6-1](#) lists all procedures to be performed at Visit 199.

Safety and tolerability monitoring during the active treatment run-in epoch

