3.1.1.3 Double-blinded randomized treatment epoch

The randomized treatment epoch will begin at Visit 201. Patients who successfully complete the run-in and tolerate LCZ696 50 mg b.i.d. will be randomized to receive LCZ696 100 mg b.i.d. or enalapril 5 mg b.i.d. for 4 weeks and be up-titrated to the target dose of LCZ696 200 mg b.i.d. or enalapril 10 mg b.i.d. in a 1:1 ratio in a double-blind manner. Please refer to [Table 6-1](#) for a detailed list of study procedures and assessment to be performed at each randomized treatment epoch visit.

The study medication will be added to the prescribed background HF therapy. Concomitant administration of ACEIs or ARBs with the study medication is strictly prohibited. Please refer to [Section 5.5.7](#) for more information on co-administration of other medications.

Reported trial outcome endpoint events will be collected as they occur throughout the randomized treatment epoch. All laboratory evaluations for planned visits after randomization

will be performed through the central laboratory or other authorized laboratory. Unscheduled laboratory assessments can be performed locally as necessary.

Visit 201 will be considered the reference visit for all study visits during the randomized treatment epoch. Regardless of the occurrence of any unscheduled visits, scheduled visits should occur within the timeframe in relation to Visit 201 as outlined in [Table 6-1](#).

Randomization Visit (Visit 201)

Patients who have met all the inclusion criteria and none of the exclusion criteria at the end of the active treatment run-in epoch will be randomized to either LCZ696 100 mg b.i.d. or enalapril 5 mg b.i.d. in a 1:1 ratio.

Site personnel should instruct the patient to refrain from taking their run-in medication on the day of Visit 201. Site personnel will document the date and time of the last dose of the LCZ696 run-in medication. This is necessary to ensure a 36-hour wash-out period to avoid overlapping of LCZ696 with enalapril and minimize the potential risk of occurrence of angioedema.

If appropriate, the patient will start to take the double-blind study medication (LCZ696 100 mg b.i.d. or enalapril 5 mg b.i.d.) the day after Visit 201. For example, if a patient's Visit 201 is on Wednesday, he/she must not take any doses of the LCZ696 50 mg b.i.d. run-in medication after Tuesday evening. The patient will then start taking the first dose of the double-blind study medication on Thursday morning.

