9.5.1.3 NYHA classification

In the core part, the change from randomization to each of the post-randomization visits in NYHA classification will be analyzed using Cochran-Mantel-Haenszel test for different row (treatment) means, stratified for screening NT-proBNP classification, based on the modified ridit scores which are also referred to as the standardized mid-ranks.

In the OLE epoch, the change from baseline (Visit 301) to each of the post baseline visits in NYHA classification will be summarized. FAS-Ext will be used, and analyses will be done by the treatment arm in the double-blind treatment epoch. Additionally, analyses will be repeated for subset of FAS-Ext with only patients in the LCZ arm of the double-blind treatment epoch, throughout the period from run-in epoch to OLE epoch using Visit 101 as baseline.

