For reference, same analysis will be performed for enalapril treatment arm to characterize the effects of enalapril dosages (5 mg b.i.d., 10 mg b.i.d.).

In the OLE epoch, for biomarkers, descriptive summary statistics (mean, median, standard deviation, min, max, Q1, Q3, geometric mean, 95% CI for geometric mean) for the change from baseline (Visit 301) to each post-baseline visit will be presented. FAS-Ext will be used, and analyses will be done by the treatment arm in the double-blind treatment epoch. Additionally, analyses in NT-proBNP will be repeated for subset of FAS-Ext with only patients in the LCZ arm of the double blind treatment epoch, throughout the period from run-in epoch to OLE epoch biomarker visits (Visits 301, 302, 303, 304 and 306) using Visit 101 as baseline.

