Change from baseline (Visit 301) of lab parameters, vital signs and ECG will be summarized as given above. Shift from baseline of ECG data will be presented using shift table. FAS-Ext will be used, and all analyses will be done for total, and by the treatment arm in the double-blind treatment epoch. Additionally, all analyses will be repeated for subset of FAS-Ext with only patients in LCZ arm of double blind treatment epoch, throughout the period from run-in epoch to OLE epoch using Visit 201 as baseline.

[figure not shown]
Proportion of patients reaching target dose level 3 of LCZ696 at Week 8 and maintained at Month 4 will be presented. FAS-Ext will be used, and analyses will be done for total, and by the treatment arm in the double-blind treatment epoch.

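### Section 9.5.2 summarises laboratory, vital-sign and ECG change from the run-in onwards, but takes as baseline Visit 201, which follows two weeks of LCZ696

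*Protocol*

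**What the plan says.** The last part of Protocol Section 9.5.2 describes the safety analyses of the open-label extension. Changes in laboratory values, vital signs and ECG are first summarised from Visit 301 in the FAS-Ext. The same analyses are then repeated for FAS-Ext patients from the LCZ696 arm, "throughout the period from run-in epoch to OLE epoch using Visit 201 as baseline".

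The position of Visit 201 relative to exposure is set elsewhere:

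- Section 3.1.1.2, on starting the run-in: "they will attend Visit 101 approximately one to two weeks after Visit 1 to start LCZ696 50 mg b.i.d. for 2 weeks".
- Section 3.1.1.3, on Visit 201: "Patients who successfully complete the run-in and tolerate LCZ696 50 mg b.i.d. will be randomized".
- The Visit 199 footnote to Table 6-1 says that the vital signs and laboratory values used for randomization are the ones recorded at Visit 199, the end-of-run-in visit.

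The same subset and period appear in three other places:

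- Section 9.5.1.3 (NYHA): "throughout the period from run-in epoch to OLE epoch using Visit 101 as baseline".
- Section 9.5.1.10 (NT-proBNP): "throughout the period from run-in epoch to OLE epoch biomarker visits (Visits 301, 302, 303, 304 and 306) using Visit 101 as baseline".
- Section 9.5.2 (AEs and SAEs): "subset of FAS-Ext with only patients in LCZ arm of double blind treatment epoch, throughout the period from run-in epoch to OLE epoch", where no baseline value is needed.

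For the run-in itself, Section 9.5.2 promises only that "the AEs, SAEs, and reasons for active run-in failures will be summarized for the active run-in epoch".

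**The concern.** The stated period and the stated baseline do not match. A change summary said to start at the run-in needs a reference value from before the run-in drug. The one named was taken after two weeks on that drug, so whatever LCZ696 did to blood pressure, potassium, creatinine or the ECG in those weeks sits in the baseline and drops out of the change.

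This matters because one extension objective in Section 2.2.3 is long-term safety and tolerability of LCZ696 over the whole study. Section 9.5.2 also lists hypotension, hyperkalemia and renal dysfunction among the safety variables. Its run-in summary covers events and reasons for run-in failure, not measured values. The protocol therefore names no change summary that shows these measurements over the first two weeks of treatment. A reader of a table labelled as running from the run-in would reasonably assume that it does.

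**Working it through.** No figure is stated in the protocol on this point, so the check sets the schedule beside the baseline rule.

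**1. Which assessments bracket the run-in.** Sources: Table 6-1 and its footnotes, Sections 6.5.1, 6.5.4 and 6.5.5.

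| Variable | Last scheduled value before LCZ696 | Value after LCZ696 starts and before the first randomized dose | Baseline as written |
|---|---|---|---|
| Vital signs | Visit 101 | Visit 199 | Visit 199 (standing for Visit 201) |
| Laboratory panel | Visit 1 | Visit 199 | Visit 199 (standing for Visit 201) |
| ECG | Screening tracing (Visit 1, or up to 6 months earlier) | Visit 201 | Visit 201 |

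The third and fourth columns coincide. The on-run-in assessments are the baseline, so 0 of 3 can appear as a change from it. With the second column as baseline, 3 of 3 can.

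**2. Consistency within the protocol.** The period wording is used four times for this subset. Three of the four name a baseline: Visit 101 twice (NYHA, NT-proBNP) and Visit 201 once (laboratory, vital signs, ECG). No reason is given for the difference.

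**3. Outputs that depend on the baseline.** These are the change-from-baseline tables, the "shift tables using extended normal ranges (baseline to most extreme post-baseline value", and the notable-value flags, which Appendix 1 defines as percent change from baseline. The flags are included on the reading that repeating all analyses as described above covers them. The change and shift tables are affected on any reading.

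**4. Size in the mean-change tables.** The amount missing equals the mean run-in change. The protocol gives no value for it.

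**5. Size in the flags, under assumption.** Let c be the Appendix 1 cut-off and r an assumed percent change over the run-in. A flag raised against the Visit 199 value corresponds to a rise since before LCZ696 of (1 + c)(1 + r) − 1.

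| r (assumed) | Creatinine, c = 50% | Potassium, c = 20% |
|---|---|---|
| −5% | 1.50 × 0.95 − 1 = 42.5% | 1.20 × 0.95 − 1 = 14% |
| 0 | 50% | 20% |
| +5% | 1.50 × 1.05 − 1 = 57.5% | 1.20 × 1.05 − 1 = 26% |
| +10% | 1.50 × 1.10 − 1 = 65% | 1.20 × 1.10 − 1 = 32% |

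**6. What the protocol itself permits.** Exclusion criterion 7 (Section 4.2) bars randomization only if eGFR falls by more than 35% between Visit 1 and Visit 199. Take an assumed eGFR of 60 at Visit 1. A fall to 39 is (60 − 39)/60 = 35% and is still allowed. If eGFR then stays at 39, the change from the written baseline is 0%, against −35% from Visit 1. By the formula in Section 6.5.4.3, at constant age, the matching creatinine ratio is 0.65^(−1/1.094) ≈ 1.48, a rise of about 48%. This is a permitted extreme, not an expected effect.

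**The case against.** The strongest case for the text is that Visit 201 follows the protocol's own rule. Section 9.2 defines core baseline as the last value before the first randomized dose, and Appendix 5 measures renal decline after randomization from Visit 199. The schedule also explains the contrast with NYHA and NT-proBNP: both are recorded at Visit 101, whereas the full laboratory panel and the ECG are not. Apart from screening, Visit 199/201 is the only point at which all three safety variables are available close together. This explains the choice but does not make it fit the stated period. Section 9.2 allows exceptions, and Appendix 5 serves patient management after randomization, not a summary said to include the run-in.

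A second objection is that a Visit 201 baseline does not forbid tabulating Visit 101 minus baseline, which is the run-in change with its sign reversed. For vital signs that is arithmetically possible, since Visit 101 belongs to the run-in epoch. It is not what the section describes. It also cannot help for laboratory values or ECG, whose only pre-exposure values come from screening, outside the stated period. Section 6.5.2 says vital signs are taken at every visit. If so, a separate Visit 201 reading would exist, but it too would follow the run-in.

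Three points stand. The flag figures rest on assumed run-in changes. A statistical analysis plan, not seen here, could add a run-in change table. A pre-exposure baseline has weaknesses of its own, set out under the fix.

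**Conclusion.** The point holds. Section 9.5.2 fixes a post-exposure baseline for a summary said to start with exposure, so the change and shift tables cannot show what happened during the run-in. A later analysis plan could add a table, but the contradiction lies in the protocol's wording.

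The structural size is certain: 0 of 3 on-run-in assessments can appear as a change, against 3 of 3 with a pre-exposure baseline. The numerical size is unknown. The flag cut-offs in the working show direction and scale under assumed run-in changes only.

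The reach is limited. This is a descriptive, single-arm summary in patients who entered the extension, with no formal inference. Raw-value summaries, AE and SAE counts, the primary analysis and the randomized comparison do not change. Run-in failures are absent whichever baseline is used. It should be corrected, but it does not threaten the trial's main conclusions.

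**What to change.** In Section 9.5.2, replace the Visit 201 baseline for this subset with the last non-missing value before the first run-in dose of LCZ696. Add one sentence saying what that means by schedule: Visit 101 for vital signs, Visit 1 for laboratory values, and the screening tracing for ECG, noting that the tracing may be up to 6 months older than Visit 1. Keep change from Visit 199/201 as a secondary summary, labelled as an on-treatment baseline, for continuity with Section 9.2.

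The downsides should be stated in the text. One common anchor becomes three. Visit 1 laboratory values are taken on the prior ACEI or ARB, while Visit 101 falls on a day when that drug is withheld (Section 3.1.1.1). Changes from these anchors therefore also carry the switch of background drug and some elapsed time. Visit 1 is nevertheless already the protocol's reference for run-in eGFR change (criterion 7).

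If the sponsor prefers Visit 201 as the only baseline, the alternative is to restate the period as starting at randomization and not to describe the summary as covering the run-in.

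The cost is one phrase and one sentence, or one phrase under the alternative. No new assessment is needed.
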